16.5. Efficacy

16.5.1. Analysis Population

The Efficacy Analysis Population will include all subjects who receive >1 dose of bemcentinib (Full Analysis Set).

Any patient who continues treatment with bemcentinib beyond confirmed disease progression will be followed for efficacy assessments (hematology testing, physical examinations and bone marrow biopsy, if clinically indicated), as defined in protocol section 13.

For the Per Protocol analysis set, the population will be defined as follows:

Patients that

- Meet key eligibility criteria, have assessable disease at baseline and have at least one post-baseline response assessment
- Have received >1 dose of bemcentinib (and combination agent in Part B2, B3 and B5)

16.6. Pharmacokinetics

16.6.1. Analysis Population

The Pharmacokinetics Analysis Population will include all patients who receive ≥ 1 dose of bemcentinib and have evaluable PK data available.

16.6.2. Methods of Analysis

The PK parameters listed in Table 15 (but not limited to) will be derived from the relevant concentration data of bemcentinib in each part of the study, derived from a PK model. Full details of the PK methodology will be written in a PK Analysis Plan.

Table 15: Plasma PK parameters

C_{max}	The observed maximum plasma concentration after single dose administration
t_{max}	The time to reach C_{max}
$AUC_{0-\tau}$	The area under the curve within a dosing interval, calculated by the linear up-log down trapezoidal method.
λ_z	The apparent terminal rate constant estimated from individual linear regression of the terminal part of the log concentration vs. time curve
$t_{1/2}$	The apparent terminal half-life, calculated by $0.693/\lambda_z$

Where possible, individual, mean and median bemcentinib plasma concentration-time data will be presented in tabular and/or graphical form.

16.7. Pharmacodynamics

16.7.1. Analysis Population

The Pharmacodynamic Analysis Population will include all patients who receive ≥ 1 dose of bemcentinib and have ≥ 1 pharmacodynamic sample collected for analysis.

16.7.2. Methods of Analysis

All pharmacodynamic biomarkers will be listed and summarized by dose cohort and time-point as appropriate. No formal statistical analysis will be performed, although descriptive terms will be used to describe the results.

16.8. Safety Monitoring Committee

No formal statistical interim analyses are planned.

Data will be monitored by the SMC, in an on-going manner, to assess patient safety as outlined in Section 9.2.1.1. During Part A, the SMC will be responsible for:

- Reviewing the safety data from Cycle 1 of each dose cohort to determine whether dose escalation can proceed
- Determining the MTD prior to commencing Part B
- Defining the starting dose of bemcentinib to be administered with cytarabine/decitabine in Part B2/Part B3.

During the execution of Part B the SMC will convene after every 10 patients have completed Cycle 1 of treatment or 6 months have elapsed, whichever occurs first. Part A and Part B3 have been fully completed (i.e. last patient last visit has been achieved in both parts). Enrolment in Part B2 has been completed with a number of patients ongoing, whereas Parts B1, B4 and B5 continue to enroll as of 17 Mar 2020.

Independent Data Monitoring Committee (IDMC) has been established since 30 Oct 2019 at the request of The Federal Institute for Drugs and Medical Devices (BfArM). During execution of the remainder of Parts B1, B2, B4 and B5, patient safety data will be monitored and assessed by the IDMC in an on-going manner in accordance with the IDMC charter.

16.9. Sample Size Considerations

Part A of the study follows a conventional algorithm (3+3 patients per dose level) to identify the MTD, escalating on 0/3 or 1/6 patients experiencing a DLT. Under this design, there is a 71% chance of escalation if the true but unknown rate of DLT is 20%, and <50% chance of escalation if the true but unknown rate of DLT is >30%. The operating characteristics of this 3+3 design are outlined in Table 16.

Table 16: Operating Characteristics of the 3+3 Study Design

True but Unknown Rate of DLT (%)	Probability of Escalation (%)
20	71
30	49
40	31
50	17
60	8

The total sample size of Part A depends upon whether DLT(s) is experienced at a given dose level (i.e. whether 3 or 6 patients have been treated) and how many dose levels are tested in order to reach the MTD. A minimum of 6- 10 patients will be treated at the MTD.

The sample size of up to 14 evaluable patients for Parts B1, B2, B3 and B4 and up to 20 evaluable patients in Part B5 in this study has been calculated on the basis of the following assumptions for a one-sided, within-group test of proportions, comparing an anticipated ORR of $\geq 20\%$ against the null hypothesis rate of 5%, with power 80% for a test of size 0.2. This calculation is based on statistical significance at the 0.2 level, since this will be taken as evidence of a trend worthy of further study. Although this is offered as a formal sample size calculation, it is acknowledged that for this early-stage study the analyses will be exploratory in nature, and that no account has been taken of multiplicity inherent in the assessment of several, presumably non-independent criteria, for ORR.

16.10. Clinical Study Report

The results of the study will be presented in an integrated CSR according to ICH guidelines.

17. Ethical Requirements

17.1. Good Clinical Practice Statement

The clinical study will be performed in accordance with the protocol, the Declaration of Helsinki, ICH Guidelines, GCP, the European Union (EU) Clinical Trials Directive (CTD) 2001/20/EC Guideline for GCP CPMP/ICH/135/95, and all applicable local regulatory requirements.

Authorization of a Clinical Trial Application, IND, or equivalent will be obtained from the relevant Regulatory Authority prior to initiation of the study within a specific country.

17.2. Ethics Committee

The final study protocol and ICF must be approved, in writing, by the relevant REC/IRB before patient enrolment commences.

The following information should be reported to the REC/IRB during the study:

- All amendments to the research (substantial and non-substantial amendments)
- Annual progress reports
- Individual SUSARs
- DSUR on an annual basis
- Urgent Safety Measures

The investigator/designee must notify the REC/IRB within 90 days of completion of the study. However if the study is terminated prematurely, written explanation of the reason(s) for the early termination must be provided within 15 days.

17.3. Patient Information and Consent

Prior to performing any study-related activities, including screening tests and procedures, written informed consent must be obtained from the patient, in accordance with local regulations.

The ICF must be in accordance with the principles that originated in the Declaration of Helsinki, current ICH and GCP guidelines, applicable regulatory requirements and sponsor policy and must be approved by the reviewing REC/IRB.

17.4. Subject Data Protection

Personally identifiable information (PII) i.e. identifiable information from or about an individual will not be collected by the sponsor. The collection and processing of personal data from patients enrolled in this study will be limited to those data that are necessary to investigate the efficacy, safety, tolerability, quality and utility of the IMP used in this study. These data must be collected and processed with adequate precautions to ensure confidentiality and compliance with applicable data privacy protection laws and regulations.

The ICF must explain that identifying information will be kept on file and that portions of the patient's medical records pertinent to the study will be reviewed by sponsor personnel (or their designees) and possibly by Regulatory Agencies and the REC/IRB for data verification purposes.

18. Administrative Procedures

18.1. Quality Assurance

In compliance with GCP and regulatory requirements, the sponsor/designee, external Regulatory Agency and/or REC/IRB may conduct quality assurance (QA) audits at any time during or following completion of the study. The investigator will be expected to cooperate with any audit and to provide assistance and documentation (including source data) as requested.

18.2. Case Report Form and Source Document Verification

Electronic CRFs will be provided for recording clinical data. Designated site personnel will record data in the eCRF for observations, tests and assessments as specified in the protocol. The investigator must permit direct access to designated source documentation (e.g. medical records) for the purpose of verifying that the data recorded in the eCRF are consistent with the original source data.

18.3. Study Monitoring

Before a patient can be screened for enrolment into the study, the sponsor/designee will conduct a study initiation visit to:

- Determine that the site facilities are adequate
- Discuss responsibilities with regard to the protocol with the investigator and study team
- Conduct training on completion of the eCRF and other study related documentation
- Review study procedures

During the conduct of the study, the sponsor/designee will provide support to the investigator and study team via telephone/e-mail communication. The sponsor/designee will conduct regular site visits, according to applicable ICH and GCP guidelines, to:

- Confirm the facilities remain acceptable
- Confirm the site study team are adhering to the protocol and regulatory requirements
- Confirm that the IMP is being properly maintained and accountability records are accurate and current
- Confirm data are being accurately recorded in the eCRF by performing source document verification

18.4. Notification of Serious Breaches

In accordance with Regulation 29A of the Medicines for Human Use (Clinical Trials) Regulations 2004 and its amendments the sponsor of the trial is responsible for notifying the Regulatory Authorities in writing, within 7 days, of any serious breach of:

- The conditions and principles of GCP in connection with the study
- The protocol relating to the study

Whilst under investigation, the site is requested to cooperate with the sponsor/designee in providing sufficient information to report the breach to the Regulatory Authorities where required, and in undertaking any corrective and/or preventive action.

18.5. Retention of Study Data

A copy of all records and essential documents must be retained in the study files for a minimum of two years following the last approval of the drug in an ICH region and until there are no pending or contemplated marketing applications in an ICH region, or a minimum of two years have elapsed since the formal discontinuation of the clinical development of the drug. No documents should be destroyed without prior written agreement between the sponsor and the investigator.

Should the investigator wish to assign the documents to another party or move them to another location, the sponsor must be notified. The sponsor will notify the investigator in writing when the study-related documents are no longer needed.

18.6. Use of Information and Publication Policy

All information regarding bemcentinib and the sponsor's operations (e.g. patent applications, formulas, manufacturing processes, basic scientific data, or formulation information) supplied by the sponsor to the investigator and not previously published is considered confidential. This confidential information remains the sole property of the sponsor and shall not be disclosed to others without the written consent of the sponsor. The investigator agrees to use this information only to perform this study and will not use it for other purposes including publications and presentations without the sponsor's written consent. The full terms of confidentiality, intellectual property and publication policy are detailed in the current Clinical Trial Agreement between the sponsor and the site.

18.7. Contract Research Organizations

Monitoring, data management, statistics and programming, medical writing, auditing and QA services will be outsourced to the sponsor's CRO Covance

Pharmacovigilance services will be outsourced to Syneos Health

PK and pharmacodynamics analyses will be outsourced to the sponsor's Bioanalytical services vendor.

18.8. Changes to the Final Study Protocol

All protocol amendments must be submitted to the REC/IRB and, if applicable, to the Regulatory Authorities.

Protocol amendments that affect patient safety, the scope of the investigation, or the scientific quality of the study should not be implemented without prior Regulatory Authority/REC/IRB approval (where applicable), except where necessary to eliminate immediate hazards to the patients.

18.9. Investigator Responsibilities

By signing the protocol, the investigator agrees to:

- Conduct the study in accordance with the protocol and make changes only after notifying the Sponsor, except to protect the safety, rights or welfare of patients
- Personally conduct or supervise the study
- Inform any patients enrolled in the study that the drug is being used for investigational purposes
- Ensure that the requirements relating to obtaining informed consent and REC/IRB review and approval meet Federal guidelines, as stated in 21CFR50 and 21CFR56
- Report to the Sponsor any AEs that occur during the course of the study, in accordance with 21CFR312.32, as well as ICH guidelines
- Have read and understood the IB for bemcentinib, including potential risks and side effects of the drug
- Ensure that all associates, colleagues and employees assisting in the conduct of the study are informed about their obligations in meeting the above commitments
- Maintain adequate and accurate records, in accordance with 21CFR312.62 and to make those records available for inspection by the sponsor, their designated

BGBC003 v10.0 (US);

representative, relevant Regulatory Authorities/REC/IRB or any agency authorized by law

- Ensure that a REC/IRB that complies with the requirements of 21CFR56 will be responsible for initial and continuing review and approval of the clinical study
- Report promptly to the REC/IRB and the sponsor all changes in the research activity and all unanticipated problems involving risks to subjects or others (to include protocol amendments and IND safety reports)
- Not make any changes in the research study without approval, except when necessary to eliminate hazards to the subject/subjects
- Comply with all other requirements regarding the obligations of the clinical investigators and all other pertinent requirements listed in 21CFR312

19. References

Appendix 3: Drugs Associated with a Risk of QT Prolongation and Cardiac Arrhythmias

For any concomitant medication, please check the following website for the drug's Torsades de Pointes (TdP) risk: <https://crediblemeds.org/oncosupport/>. Drugs with known TdP risk should be avoided. For drugs with a conditional risk, please review the product label and correct any abnormalities, e.g. hypokalemia.

Known Risk of TdP	Substantial evidence supports the conclusion that these drugs prolong the QT interval AND are clearly associated with a risk of TdP, even when taken as directed in official labelling.
Possible Risk of TdP	Substantial evidence supports the conclusion that these drugs can cause QT prolongation BUT there is insufficient evidence at this time that these drugs, when used as directed in official labelling, are associated with a risk of causing TdP.
Conditional Risk of TdP	Substantial evidence supports the conclusion that these drugs are associated with a risk of TdP BUT only under certain conditions (e.g. excessive dose, hypokalemia, congenital long QT or by causing a drug-drug interaction that results in excessive QT interval prolongation)

Generic Name	Brand Name
Amiodarone	Coradone/Pacerone
Anagrelide	Agrylin®, Xagrid®
Arsenic trioxide	Trisenox
Astemizole	Hismanal
Azithromycin	Zithromax®, Zmax®
Bepridil	Vascor
Chlorquine	Arelan
Chlorpromazine	Thorazine
Cisapride	Propulsid
Citalopram	Celexa®, Cipramil®
Clarithromycin	Biaxin
Cocaine	Cocaine
Disopyramide	Norpace
Dofetilide	Tikosyn
Domperidone	Motilium
Dronedarone	Multaq®
Droperidol	Inapsine
Erythromycin	Erythrocin/E.E.S.
Escitalopram	Cipralex®, Lexapro®
Flecainide	Tambocor®, Almarytm®
Halofantrine	Halfan
Haloperidol	Haldol
Ibutilide	Covert
Levomethadyl	Orlaam
Mesoridazine	Serentil
Methadone	Methadose/Dolophine
Moxifloxacin	Avelox
Ondansetron	Zofran®, Anset®

Petamidine	NebuPent/Pentam
Pimozide	Orap
Probucol	Lorelco
Procainamide	Pronestyl/Procan
Propofol	Diprivan
Quinidine	Cardioquin/Quinaglute
Sevoflurane	Ulane®, Sojourn®
Sotalol	Betapace
Sparfloxacin	Zagam
Sulpiride	Dogmatil®, Dolmatil®
Terfenadine	Seldane
Thioridazine	Mellaril
Vandetanib	Zactima

Woosley RL, Heise CW, Gallo T, Tate J, Woosley D and Romero KA, www.CredibleMeds.org, QTdrugs List, [Accession Date], AZCERT, Inc. [name]

Appendix 4: CYP3A4 Substrates

Examples of CYP3A4 substrates are provided below. For most up-to-date information on CYP3A4 substrates, please check the Drug Interactions Flockhart Table™ <https://drug-interactions.medicine.iu.edu/Main-Table.aspx>.

University of Indiana CYP3A4, 5, 7 P450 Drug Interactions Abbreviated "Clinically Relevant" Table of Substrates

Macrolide antibiotics:	HIV Antivirals:	HMG CoA Reductase Inhibitors:
clarithromycin	indinavir	atorvastatin
erythromycin (not 3A5)	ritonavir	lovastatin
NOT azithromycin	saquinavir	NOT pravastatin
telithromycin	nevirapine	NOT rosuvastatin
		simvastatin
Anti-arrhythmics:	Prokinetics:	
quinidine→3-OH	cisapride	Others:
		alfentanyl
Benzodiazepines:	Antihistamines:	aripiprazole
alprazolam	astemizole	boceprevir
diazepam→3OH	chlorpheniramine	buspirone
midazolam	terfenadine	carbamazepine
triazolam	Calcium Channel Blockers:	gleevec
	amlodipine	haloperidol
Immune Modulators:	diltiazem	pimozide
cyclosporine	felodipine	quinine
tacrolimus (FK506)	nifedipine	tamoxifen
sirolimus	nisoldipine	telaprevir
	nitrendipine	trazodone
PDE-5 Inhibitors:	verapamil	vincristine
sildenafil		diergotamine & ergotamine
tadalafil		fentanyl
ildenafil		

Flockhart DA. Drug Interactions: Cytochrome P450 Drug Interaction Table. Indiana University School of Medicine (2007). "/clinpharm/ddis/clinical-table/" Accessed 20 October 2016.

Appendix 5: Modified International Working Group Response Criteria in Acute Myeloid Leukemia (Cheson, 2003, Döhner, 2017)

IWG Response Criteria in AML		Bone Marrow Blasts/Myeloblast	Circulating or Peripheral Blood Blasts ^a	Absolute Neutrophil Count	Platelet Count	EMD
Morphologic Complete Remission	CR	<5% and no myeloblasts with Auer rods	None	$\geq 1.0 \times 10^9/L$ or $\geq 1,000/\mu L$	$\geq 100 \times 10^9/L$ or $\geq 100,000/\mu L$	None
CR with Incomplete Blood Count Recovery	CRi	<5% and no myeloblasts with Auer rods	None	$<1.0 \times 10^9/L$ or $<1,000/\mu L$	$<100 \times 10^9/L$ or $<100,000/\mu L$	None
Morphologic leukemia-free state	MLFS	<5% and no myeloblasts with Auer rods ^b	No hematologic recovery required			None
Partial Remission	PR	Decrease of myeloblasts % to 5% to 25% and decrease of pretreatment myeloblast % by at least 50%	All hematologic criteria of CR			
Unchanged	UN	Absence of CR, CRi or PR and criteria for PD not met				
Progressive Disease ^c	PD	>50% increase in myeloblasts over the pretreatment value (a minimum 15% increase is required if <30% myeloblasts pretreatment)	>50% increase in PB to $>25 \times 10^9/L$ or $>25,000/\mu L$ ^d			New EMD disease

a. PBs are quantified as an automated WBC times percentage of blasts by manual differential (100 cells) per standard clinical laboratory procedures.
 b. BM examination should not be aplastic, and have at least 200 cells or cellularity should be at least 10%
 c. PD is usually accompanied by a decline in ANC and platelets, increased transfusion requirement and decline in performance status and increase in symptoms.
 d. Certain targeted therapies may cause a differentiation syndrome, that is, a transient increase in the percentage of BM blasts (myeloblasts) and an absolute increase in PBs; in the setting of therapy with such compounds, an increase in blasts may not necessarily indicate PD.

Abbreviations: AML, acute myeloid leukemia, ANC, Absolute Neutrophil Count; BL, EMD, Extramedullary Disease; IWG, International Working Group, PB, Peripheral Blood Blast; WBC, White Blood Cell.

References

BGBC003 v10.0 (US);

Appendix 6: International Working Group Response Criteria in Myelodysplastic Syndromes (Cheson, 2006)

Category A: Altering the natural history of disease			
IWG Response Criteria in MDS	Bone Marrow ^a	Peripheral Blood ^a	Additional Considerations
Complete Remission (CR)	≤5% myeloblasts with normal maturation of all cell lines with no evidence for dysplasia ^b	Normalization of blood counts as defined by: 
 • Hb ≥11g/dL (not supported by EPO or transfusions) • Platelets ≥100 x 10⁹/L or 100,000/µL (not supported by transfusions) • Neutrophils ≥1.5 x 10⁹/L or 1,500/µL (not supported by G-CSF) • PB 0% 	Responses to be confirmed in two successive assessments; response parameters in peripheral blood needs to be maintained for at least 6 weeks.
Partial Remission (PR)	All CR criteria met if abnormal before treatment except for: 
 • Myeloblasts decrease by 50% or more over pretreatment value but still >5%, or • Less advanced FAB or IPPS category compared to pretreatment value 	Hematologic improvement	Absolute values must last at least 6 weeks.
Marrow CR	≤5% myeloblasts and decrease by ≥50% over pretreatment value	If hematologic improved, these should be noted in addition to marrow CR (see Category B).	
Stable Disease (SD)	Failure to achieve at least PR, but no evidence of PD for at least 3 treatment cycles.		
Progressive Disease (PD)	
 • For patients with less than 5% myeloblasts: a 50% or more increase in myeloblasts to more than 5% myeloblasts. • For patients with 5% to 10% myeloblasts: a 50% or more increase to more than 10% myeloblasts. 	Myeloblast increase plus at least one of the following: 
 • ≥50% decrease in ANC or platelets • Reduction in Hb by ≥2g/dL • Transfusion dependence. 	Death during treatment

	
 For patients with 10% to 20% myeloblasts: a 50% or more increase to more than 20% myeloblasts. For patients with 20% to 30% myeloblasts: a 50% or more increase to more than 30% myeloblasts. 		
Relapse after CR or PR	
Relapse is characterized by at least one of the following:
 
 Return to pretreatment myeloblasts percentage ≥50% decrease in ANC or platelets 
Reduction in Hb by ≥2g/dL or transfusion dependence.
		
Disease transformation	
Transformation to AML (30% or more blasts).
		
Category B: Hematologic Improvement (HI)			
	Hematopoietic Lineage	Response Criteria	Definition ^a
	Erythroid (HI-E)	Major response	For patients with pretreatment Hb<11 g/dL, greater than 2 g/dL increase in Hb; for RBC transfusion-dependent patients, transfusion independence.
		Minor response	For patients with pretreatment Hb <11 g/dL, 1 to 2 g/dL increase in Hb; for RBC transfusion-dependent patients, 50% decrease in transfusion requirements.
	Platelet (HI-P)	Major response	For patients with pretreatment PLT counts of <100 x 10 ⁹ /L or 100,000/µL, an absolute increase of 30 x 10 ⁹ /L or 30,000/µL or more; for PLT transfusion-dependent patients, stabilization of PLT counts and PLT transfusion independence.

		Minor response	For patients with pretreatment PLT counts $<100 \times 10^9/L$ or $100,000/\mu L$, a 50% or more increase in PLT count with a net increase $>10 \times 10^9/L$ or $10,000/\mu L$ but less than $30 \times 10^9/L$ or $30,000/\mu L$.
	Neutrophil (HI-N)	Major response	For ANC $<1.5 \times 10^9/L$ or $1,500/\mu L$ before therapy, ANC increase of at least a 100%, or an absolute increase of more than $0.5 \times 10^9/L$ or $500/\mu L$, whichever is greater.
		Minor response	For ANC less than $1.5 \times 10^9/L$ or $1,500/\mu L$ before therapy, ANC increase of at least 100%, but absolute increase less than $0.5 \times 10^9/L$ or $500/\mu L$.

Category C: Cytogenetic Response (CRc)^b

	Major CRc	No detectable cytogenetic abnormality, if preexisting abnormality was present.
	Minor CRc	$\geq 50\%$ reduction of abnormal metaphases

a. Improvements in BM and PB must be based on ≥ 2 successive assessments; response in PBN must be maintained for at least 6 weeks.
 
b. IWG criteria require 20 analyzable metaphases assessed by conventional cytogenetic studies to diagnose or exclude the presence of a cytogenetic abnormality. For normal Karyotype, 20 metaphases are optimal to ensure that enough metaphases have been examined. For cytogenetic response, 20 metaphases are optimal, but not necessary, to define the degree of cytogenetic response. FISH to assess changes in a specific cytogenetic abnormality is acceptable.
		

Abbreviations: AML, acute myeloid leukemia; ANC, absolute neutrophil count; EPO, erythropoietin; G-CSF, FAB, French-American-British (classification system); IPSS, International Prognostic Scoring System; granulocyte colony stimulating factor; Hb, hemoglobin; IWG, International Working Group; MDS, myelodysplastic syndrome; PB, peripheral blast; PLT, platelet; RBC, red blood cell.

Reference

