### 3.2 Efficacy endpoints

In AML, efficacy endpoints will be measured using objective response criteria, in evaluable patients.

- Objective Response (OR) or Stable Disease (SD) according to the revised recommendations of the International Working Group (IWG) in AML [Cheson, BGBC003 v8.0 (NO); 04 August 2020 CONFIDENTIAL Page 37 of 113 2003 and Döhner, 2017] (see Appendix 5 of the protocol). SD is defined as having unchanged disease for at least 3 treatment cycles.
- Proportion of patients with an OR + SD as an estimate of clinical benefit.
- Relapse Free Survival
- Event Free Survival
- Overall Survival
- To explore the correlation between baseline biomarker levels and clinical endpoints

In MDS, efficacy endpoints will be measured using the following response criteria.

- OR or SD according to the revised recommendations of the IWG in MDS (see Appendix 6 of the protocol). SD is defined as failure to achieve at least PR but not evidence of PD for at least 3 treatment cycles.
- Proportion of patients with an OR + SD as an estimate of clinical benefit.
- Relapse Free Survival
- Event Free Survival
- Overall Survival
- To explore the correlation between baseline biomarker levels and clinical endpoints

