## 5.7 Efficacy Analysis

The endpoints to be analysed in the efficacy analysis are:

**Objective response rate [ORR]** : Proportion of patients with a best objective response such as, CR (Complete Remission), Cri (Complete Remission with Incomplete hematologic Recovery), CRp (Complete Remission with Incomplete Platelet Recovery), CRh and PR(Partial Remission) for AML patients and CR, PR, MR(Marrow Response), PMR(Partial Marrow Response) for MDS patients;

CRh is defined as, CR (<5% myeloblasts and 0% blasts in the peripheral blood) with partial hematologic recovery, defined as meeting CR criteria but with ANC > 0.5 10^9/L and platelets > 50 10^9/L responses for patients with AML.

Best Objective Response (BOR) = Best response obtain during the study participation for a patient;

**Disease control Rate (Objective Response + SD) [DCR]**: Proportion of patients with a best objective response such as, CR, CRi, CRp, CRh and PR for AML patients and CR, PR, MR, PMR for MDS patients, + SD (stable disease) as an estimate of clinical benefit;

The ORR will be summarized by;

- Age group (<75 years, >= 75);
- AML Disease Cytogenetic Profile (Favourable, Intermediate, Adverse and not done);

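### Appendix 5 gives Partial Remission a 5% floor, so, read literally, an AML patient with CR-level counts and at least a 50% blast fall who drops below 5% with persisting Auer rods is Unchanged, while the same patient at 5% to 25% is a responder

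*Protocol*

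**What the plan says.** Protocol Appendix 5 is the AML response table. Its rows bear on this point as follows.

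- **CR, CRi and MLFS:** each carries the same marrow condition, "<5% and no myeloblasts with Auer rods" (MLFS with a footnote on marrow adequacy), and each shows no extramedullary disease (EMD).
- **PR:** the marrow condition is "Decrease of myeloblasts % to 5% to 25% and decrease of pretreatment myeloblast % by at least 50" per cent. The blood condition is "All hematologic criteria of CR", that is, no circulating blasts, neutrophils of at least 1.0 and platelets of at least 100 (x10^9/L). The EMD cell of this row is blank in the text supplied.
- **Unchanged:** "Absence of CR, CRi or PR and criteria for PD not met".
- **Progressive disease (PD):** a rise in blasts above stated limits, or "New EMD disease".

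SAP 5.7 builds the AML ORR from CR, CRi, CRp, "CRh and PR(Partial Remission) for AML patients". Unchanged is not in the list. CRp is given a name but no criteria. For CRh the SAP says "CRh is defined as, CR (<5% myeloblasts and 0% blasts in the peripheral blood) with partial hematologic recovery, defined as meeting CR criteria", with neutrophils above 0.5 and platelets above 50.

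Protocol 16.5.2 tests ORR one-sided against a 5% null and reads P<0.2 as enough of a trend to justify further study.

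**The concern.** A response scale should not rank a deeper marrow response below a shallower one when everything else is equal. Here the 5% floor on PR and the Auer-rod exclusion in the three rows below 5% leave a hole. A patient who clears the marrow to under 5% but still shows Auer rods is too good for PR and not clean enough for CR, CRi or MLFS, and so lands in the residual category.

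ORR is the only efficacy endpoint with a formal test, and Appendix 5 scores every AML cohort (A, B1, B2, B3, B5). SAP 5.7 also limits relapse-free survival to responders, so such a patient would leave that analysis too. Response is assessed by the investigator at about 20 sites. A case the table handles awkwardly may be scored PR at one site and Unchanged at another.

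**Working it through.** **Step 1. Reproduce the plan's sample size** (Protocol 16.9, SAP 4.9: null 5%, alternative 20%, one-sided 0.2, power 80%; n = 14, and 20 in B5). With X binomial(n, p), take the smallest r for which P(X≥r | 0.05) is below 0.2.

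- n=14: r=2. Power = 1 − 0.8^14 − 14×0.2×0.8^13 = 0.802.
- n=20: r=3, with power 0.794.

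Both agree with the stated 80%.

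**Step 2. Run one patient through Appendix 5.** Pretreatment blasts 60%, neutrophils 1.5, platelets 150, no circulating blasts, no EMD, Auer rods present throughout. Only the follow-up marrow percentage changes.

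| Follow-up blasts | CR, CRi, MLFS | PR | PD | Category | In ORR? |
|---|---|---|---|---|---|
| 3% | fail: Auer rods | fails: below 5% | no | Unchanged | no |
| 4.9% | fail: Auer rods | fails: below 5% | no | Unchanged | no |
| 5% | fail: not below 5% | met | no | PR | yes |
| 25% | fail: not below 5% | met | no | PR | yes |

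The order reverses at 5%.

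**Step 3. Conditions on the comparison.** The patient at 25% is PR only with at least a 50% fall (pretreatment 50% or more) and CR-level counts. From 40%, a follow-up of 25% is a fall of 15/40 = 37.5%, hence Unchanged. From 60% to 25% with neutrophils of 0.8 is also Unchanged. Likewise, removing the floor would make the 3% patient PR only if counts are at CR level.

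**Step 4. Does the SAP close the gap?** The step 2 patient clears the CRh count thresholds. The parenthesis in the CRh definition mentions only marrow and circulating blasts, but the same sentence requires the CR criteria to be met, and in Appendix 5 these exclude Auer rods. CRp has no criteria to apply. So the SAP does not clearly rescue the patient, and does not clearly exclude the patient either.

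**Step 5. What one patient does to the test.** Under p = 0.05:

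- n=14: P(X≥1) = 1 − 0.95^14 = 0.512. P(X≥2) = 0.512 − 14×0.05×0.95^13 = 0.153.
- n=20: P(X≥2) = 1 − 0.95^20 − 20×0.05×0.95^19 = 0.264. P(X≥3) = 0.264 − 190×0.05^2×0.95^18 = 0.075.

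Moving from 1 to 2 responders of 14, or from 2 to 3 of 20, crosses 0.2.

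**Step 6. Range for power (assumption).** If a share q of true responders fell in the gap, the effective ORR would be 0.20×(1−q).

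| q | Power, n=14 | Power, n=20 |
|---|---|---|
| 0 | 0.802 | 0.794 |
| 5% | 0.776 | 0.761 |
| 10% | 0.747 | 0.725 |
| 20% | 0.681 | 0.642 |

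The documents give no value for q. Zero is possible.

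**The case against.** The strongest reply is that the pattern is narrow. It needs under 5% marrow blasts, no circulating blasts, CR-level neutrophils and platelets, and residual Auer rods, all in one patient. No frequency is given. One patient can tip a cohort of 14 on any classification detail, the protocol calls these analyses exploratory, and an Unchanged patient is not lost altogether: "SD is defined as having unchanged disease for at least 3 treatment cycles", so that patient can still enter the disease control rate. All of this stands. It limits the size of the problem but does not put the order of the categories right.

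Second, the CRh parenthesis could be read to admit the patient. That stands as an ambiguity, and the SAP should remove it.

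Third, a reader might extend the argument to persisting EMD, since CR, CRi and MLFS exclude it and only new EMD is PD. The documents do not support this as established. It rests on a blank cell in a table read by a program, and that cell may be merged or may have lost its entry. If PR also excludes EMD, there is no reversal.

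Fourth, the data may not be there. The response-assessment footnotes to Tables 4 to 6 list blasts, neutrophils and platelets; Protocol 13.4 adds transfusion requirement. None names Auer rods. SAP Listing 16.2.8.13.1 covers marrow histology without stating its content. This stands and bears on the cost of the fix.

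Against the view that the floor is deliberate: the MDS table in Appendix 6 has a marrow CR row that catches a marrow at or below 5% without full CR. The AML table has no counterpart for the Auer-rod case. That suggests an oversight but does not prove one.

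**Conclusion.** The point holds for Auer rods. On the wording of Appendix 5, and given CR-level counts and at least a 50% fall, a marrow under 5% with Auer rods is Unchanged, while the same patient at 5% to 25% is PR and counts in ORR. CRh and CRp do not clearly repair this.

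A reader might infer that ORR is biased downward. The documents do not show that: there is an effect only if such a patient occurs, and none may. Nor does every patient who stops at 25% count as a responder; the conditions in step 3 apply. What can be said is that, for a cohort at the margin, one such patient changes the P<0.2 result (0.512 vs 0.153 at n=14; 0.264 vs 0.075 at n=20). These figures assume the full planned cohort sizes and an exact binomial test. The rule should be corrected because it gives a reversed result and is cheap to change, not because a large effect has been demonstrated.

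**What to change.** 1. In the PR row of Appendix 5 and in the SAP 5.7 derivation, add: *marrow blasts below 5% with Auer rods present, a fall of at least 50% from the pretreatment percentage, and all hematologic criteria of CR met, is classified as PR.*
2. In SAP 5.7, state that CRh and CRp require absence of Auer rods.
3. Apply the rule to all AML response records for which Auer-rod status is recorded, not only to those scored Unchanged. In an open-label, investigator-assessed study, a search limited to Unchanged records could move patients in one direction only.
4. Document the change under SAP 5.14 before database lock, and report ORR with and without any reclassified patient.
5. Separately, check the EMD cell of the PR row in the source table and state how persisting EMD is scored. Do not let it become PR by default through the new wording.

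The cost is one table cell, a short addition to the derivation and one sensitivity line. SAP section 1 pools four country protocols, so the same row should be checked in each. The downsides are an occasional extra PR, and the need for Auer-rod status to be available in the marrow records; where it is missing, the report should say so.
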